8.1.1 Nonclinical

[REDACTED]

[REDACTED]

CONFIDENTIAL

CT1812, CA35306, Final Protocol, Amendment 1_15Dec2021

[REDACTED]

[REDACTED]

[REDACTED]

[REDACTED]

[REDACTED]

[REDACTED]

CONFIDENTIAL

CT1812, CA35306, Final Protocol, Amendment 1_15Dec2021

[REDACTED]

[REDACTED]

[REDACTED]

[REDACTED]

8.1.2 Clinical

Phase I clinical trial for single ascending dose (SAD) and multiple ascending dose (MAD) studies have been completed in healthy subjects (study number COG0101). This double-blind, placebo controlled, ascending dose, multi-cohort trial included a food effect arm at the 90 mg dose.

Pharmacokinetics

In the SAD part, each cohort consisted of 6 subjects who received a single dose of CT1812 and 2 subjects who received matching placebo. Following single-dose administration (10 mg, 30 mg, 90 mg [fed and fasted], 180 mg, 450 mg, and 1120 mg), Tmax was reached in 60 to 90 minutes. The median t_{1/2} ranged from 11.1 to 14.0 hours (coefficient of variance [%CV] from 14% to 39%) across the dose groups with no dose dependence. Individual t_{1/2} ranged from 7.1 to 19.3 hours. Plasma exposure (AUC_{inf}) and Cmax were approximately dose proportional across 2 orders of magnitude. No appreciable differences in plasma AUC or Cmax were observed between fed and fasted cohorts given a 90 mg oral dose. No gender differences were detected.

In the MAD part, each cohort consisted of 8 subjects who received CT1812 and 2 subjects who received matching placebo once daily (QD) for up to 14 days. Following multiple-dose administration (280 mg and 560 mg [younger cohorts] and 560 mg [older cohort]), PK profiling was performed on samples drawn from participants on Day 3 and Day 14 of dosing. Tmax ranged from 0.5 to 4.0 hours with the median Tmax for each cohort ranging from 0.88 to 2.0 hours. The t_{1/2} ranged from 8.93 to 12.3 hours with no linear correlation with dose. Individual t_{1/2} ranged from 6.14 to 21.7 hours. Plasma exposure (AUC₀₋₂₄) and Cmax were approximately dose-proportional and showed modest accumulation compared to QD dosing in the SAD part. The healthy elderly subjects dosed with 560 mg of CT1812 for 14 days demonstrated mean plasma concentrations of CT1812 between that of the 560 mg and the 840 mg doses in healthy young subjects. Mean Cmax was 31% above, Tmax similar, and AUC₀₋₂₄ was 58% above the 560 mg dose parameters in normal healthy young subjects. Cerebrospinal fluid (CSF) was drawn from participants in the 560 mg and 840 mg cohorts 23 hours after dosing on Days 7, 8, or 9 for determination of CT1812 concentrations. Subjects dosed with 560 mg had a mean (\pm standard deviation) CSF concentration of 8.01 (4.26) ng/mL. Subjects in the 840 mg cohort had a mean CSF concentration of 23.3 ng/mL. These results indicate CNS penetration of CT1812 following oral dosing. Multiple dose exposure of CT1812 corresponded to more than 20 times the expected minimum therapeutic dose (34 to 38 mg) while CSF analysis indicated that brain concentrations exceeded the minimum target expected to improve memory (>80% receptor occupancy).

Following CT1812 (90, 280, and 560 mg) administered QD to patients with mild to moderate AD for 28 days, preliminary PK analysis showed evidence of modest accumulation of CT1812 as indicated by plasma AUC values. Both AUC₀₋₂₄ and Cmax estimates were higher on Day 28 than on Day 1, and pre-dose trough concentrations increased across the

dosing course, with steady-state levels generally attained by Day 7. Systemic exposure, as indicated by Cmax and AUC, increased approximately proportionally with dose; variability in PK parameters was high, with some individual values overlapping between dose groups. Lumbar punctures were performed on Day 28, 24 hours after the Day 27 dose. Mean steady-state predose CT1812 concentrations in the CSF increased with dose. Neurogranin levels, a synaptic damage marker that increases in the CSF of AD patients, significantly declined relative to screening levels in CT1812-treated patients by 17.6% compared to placebo-treated individuals, this finding is consistent with CT1812's mechanism of action and preclinical studies demonstrating the drug can prevent Abeta oligomer-induced synapse loss and return synapse number to normal. Synaptotagmin-1 levels, synaptic damage biomarker that is elevated in the CSF of AD patients, significantly declined by a mean of 63% in CT1812-treated patients on Day 28 compared to baseline values, whereas placebo treated values increased by a mean of 24%.

A fixed-sequence study to examine the effect of multiple-dose CT1812 administration on standard probes of CYP2C19 (Omeprazole), CYP2C9 (Tolbutamide), CYP2D6 (Dextromethorphan), and CYP3A4/5 (Midazolam) activity in healthy adult subjects was also conducted. Based on the small magnitude of change in PK parameters observed in this study for the isoenzymes CYP2D6 and CYP3A4, clinically meaningful interactions are unlikely except possibly for narrow therapeutic range CYP3A4 substrates. No significant interaction was observed for isoenzymes CYP2C19 and CYP2C9.

Safety

Single dose administration up to 1120 mg, and 14-day administration up to 840 mg/day were well tolerated. Adverse events reported to date have all been mild to moderate in severity, (with the exception of one serious adverse event [SAE] considered unrelated to study drug) and have mainly included headache, nausea, vomiting, diarrhea, constipation, abdominal pain, dyspepsia, upper respiratory tract infection, lightheadedness, syncope, myalgia, dizziness, rash, and pain at the lumbar puncture site in those subjects who had lumbar punctures. There was one SAE following the 840 mg/day dose of the MAD investigation, an upper respiratory infection believed to be unrelated to study drug. There was one subject in the MAD investigation who developed a rash and showed improvement after discontinuing CT1812. Four (4) subjects in the MAD investigation showed an increase in liver function tests (LFTs) below 3 times the upper limit of normal (including one subject receiving placebo). These abnormalities resolved after the 14-day dosing period, with the exception of one subject who had an isolated rise of LFTs at Day 35. Lymphocytopenia was observed, at approximately Day 14 of dosing, in all cases it resolved with continuation of treatment except in one subject whose resolution was associated with drug cessation related to liver function test elevation. These cases were isolated to the 560 mg QD dose, and in 75% of cases were associated with non-specific malaise, which may suggest a stress-related response.

Refer to the Investigator's Brochure (IB) for detailed background information on CT1812 ([IB, Version 5.0](#)).

8.2 Rationale

8.2.1 Rationale for this Study and Study Design

The disposition of any drug in the body is controlled by physiological processes affecting absorption, metabolism, and excretion. The most efficient and well-established approach to elucidate these processes is a mass balance study in which the drug dose is administered in radiolabeled form, followed by collection and analysis of different biological matrices for radioactivity using liquid scintillation count and determination of drug concentration using conventional liquid chromatography-tandem mass spectrometry and metabolite profile using liquid chromatography with radiometric detection. The PK, metabolic pathways, and routes of elimination of CT1812 have been evaluated in vitro and in vivo in preclinical species (IB, Version 5.0). In this study the TRA of [¹⁴C]-CT1812 will be measured using accelerator mass spectrometry (AMS).

Additionally, the PK profile of CT1812 in humans has been evaluated in healthy subjects (in a SAD and MAD investigation [Study COG0101]). Currently, the biotransformation/metabolism and excretory pathways of CT1812 in humans are not known.

The aim of this study is to characterize the plasma exposure, clearance pathways, and excretion routes for CT1812 and its metabolites in healthy male subjects following oral administration. Based on data in healthy subjects, the average t_{1/2} of CT1812 following single oral administration in the fasted state for doses from 10 mg to 1120 mg (Study COG0101) ranged from 11.1 to 14 hours, thus, it is expected that more than 90% of the radioactivity should be eliminated within 168 hours postdose, the sampling duration in this study.

8.2.2 Rationale for the Dose Selection

The single dose consisting of 300 mg (~1 μ Ci) [¹⁴C]-CT1812 oral capsules chosen for this study is expected to provide sufficient mass of drug, and sufficient specific radioactivity (using AMS analysis), for detection and analysis of parent drug and/or metabolites in whole blood, plasma, urine, and fecal samples, as applicable, with CT1812 exposures that are in a safe and pharmacologically active range. Single doses of CT1812 (10 mg – 1120 mg), administered previously to healthy subjects appeared to be safe and well tolerated with the majority of events reported being mild in severity.

The effective dose of radiation for a human male following a single oral administration of 1 μ Ci of [¹⁴C]-CT1812, was calculated to be 0.036 mrem. The effective dose is <20 x than what the average American receives in one day from natural background radiation (NCRP, 2009). Estimated radiation doses from a 1 μ Ci oral administration of [¹⁴C]-CT1812 are below the radiation dose limits set forth in 21 Code of Federal Regulations (CFR) 361 for the whole body, active blood-forming organs, lens of the eye, gonads, and any other organ. The extrapolated 0.036 mrem effective dose represents 0.0012% of the FDA limit (3000 mrem to the whole body, active blood-forming organs, lens of the eye, or gonads). Based on these results, a dose of 1 μ Ci of [¹⁴C]-CT1812 can be administered to a human and be recognized as safe under FDA guidelines (CFR Title 21, 2019).

8.3 Risks and/or Benefits to Subjects

Based on the clinical safety data available from healthy subject studies, the oral dose of CT1812 administered in this study is not anticipated to induce any potential risk or benefit to subjects participating in this study, as it is a single dose administered according to the dosing recommendations in the IB and was found to be safe and well tolerated ([IB, Version 5.0](#)).

The estimated total radiation dose and the tissue specific exposure from a single oral administration of ~1 μ Ci [^{14}C]-CT1812 are below the radiation dose limits set forth by the Food and Drug Administration (FDA) (see [Section 8.2.2](#)). Thus, the health risk resulting from exposure to radiation in the study drug is very low.

The safety monitoring practices employed by this protocol (i.e., AE questioning, 12-lead ECG, vital signs, clinical laboratory tests, ophthalmic examinations, and C-SSRS) are adequate to protect the subjects' safety and should detect all expected treatment-emergent AEs (TEAEs).

[figure not shown]
There will be no direct health benefit for study participants from receipt of study drug. An indirect health benefit to the healthy subjects enrolled in this study is the free medical tests received at screening and during the study.

9 OBJECTIVES AND ENDPOINTS

Objectives	Endpoints
Primary	
To determine the route(s) of elimination and the overall mass balance of CT1812 following a single oral dose of [¹⁴ C]-CT1812 administered in healthy adult male subjects.	TRA recovery and the percent of the radioactive dose excreted in the urine and feces.
To quantitate TRA concentration equivalents in whole blood, plasma, urine, and feces following a single oral dose of [¹⁴ C]-CT1812 administered in healthy adult male subjects.	TRA concentration equivalents in whole blood and plasma and [REDACTED] [REDACTED] [REDACTED] [REDACTED] [REDACTED] [REDACTED]
To characterize the PK profile of CT1812 and its metabolite, M6, in plasma following a single oral dose of [¹⁴ C]-CT1812 administered in healthy adult male subjects.	CT1812 and M6 metabolite concentrations in plasma and [REDACTED] [REDACTED] [REDACTED] [REDACTED]
To characterize the metabolite profile of CT1812 in plasma, urine, and feces following a single oral dose of [¹⁴ C]-CT1812 in healthy adult male subjects and identify the chemical identity of each metabolite accounting for more than 10% of circulating TRA.	CT1812 metabolite profiling and chemical identification in plasma, urine, and fecal samples containing sufficient amounts of radioactivity.

CONFIDENTIAL

CT1812, CA35306, Final Protocol, Amendment 1_15Dec2021

10 STUDY DESIGN

10.1 Overall Study Design and Plan

This is an open-label, single-dose study to assess the absorption, metabolism, excretion, and mass balance for [¹⁴C]-CT1812.

Eight (8) healthy male subjects will be enrolled.

Screening of subjects will occur within 28 days prior to dosing.

Subjects will be admitted to the [REDACTED] on Day -1 and discharged from the [REDACTED] following completion of 168 hours postdose procedures (Day 8).

On Day 1, subjects will receive a single oral dose of 300 mg CT1812 (2 capsules) with a microtracer dose of ~1 μ Ci [¹⁴C]-CT1812 (1 capsule). Whole blood, plasma, urine, and fecal samples will be collected over 168 hours postdose (Day 8) to measure TRA (all samples), CT1812 and M6 metabolite concentrations (plasma), and for metabolite profiling and identification (plasma, urine, and fecal samples).

Safety will be monitored throughout the study by repeated clinical and laboratory evaluations.

Discontinued subjects may be replaced at the discretion of the Sponsor.

10.1.1 Confinement and Follow-Up

Subjects will be housed on Day -1, at the time indicated by the [REDACTED], until completion of 168 hour procedures. Subjects may be admitted earlier than Day -1 for Coronavirus Disease-2019 (COVID-19) testing not related to study protocol as per [REDACTED] requirements. A subject may be required to remain at the [REDACTED] for longer at the discretion of the Principal Investigator (PI) or designee.

The [REDACTED] will attempt to contact all subjects who received the study drug (including subjects who terminate early) using their standard procedures approximately 14 days after dosing to determine if any AE has occurred since the last visit.

10.1.2 End of Study Definition

The end of study is defined as the date of the last scheduled study procedure, i.e., the follow-up contact, outlined in the Study Events Flow Chart ([Section 6](#)).

A subject is considered to have completed the study if he has completed the last scheduled procedure, i.e., the follow-up contact, shown in the Study Events Flow Chart ([Section 6](#)).

11 STUDY POPULATION

11.1 Inclusion Criteria

Subjects must fulfill all of the following inclusion criteria to be eligible for participation in the study:

1. Healthy, adult, male, 19-55 years of age, inclusive, at the Screening visit.
2. Male subjects must follow protocol specified contraception guidance as described in [Section 11.4.5](#).
3. Continuous non-smoker who has not used tobacco/nicotine-containing products for at least 3 months prior to dosing.
4. Body mass index (BMI) ≥ 18.0 and $\leq 30.0 \text{ kg/m}^2$ at the Screening visit (subjects must not have experienced a weight loss or gain of $>10\%$ within 4 weeks of dosing).
5. Medically healthy with no clinically significant medical history, physical examination, laboratory profiles, vital signs or ECGs, as deemed by the PI/designee at the Screening visit.
6. History of a minimum of 1 bowel movement per day.
7. Able to swallow multiple capsules.
8. Understands the study procedures in the informed consent form (ICF), and be willing and able to comply with the protocol.

11.2 Exclusion Criteria

Subjects must not be enrolled in the study if they meet any of the following criteria:

1. Evidence of disease that, in the opinion of the PI/designee, may influence the outcome of the study within 4 weeks before dosing; e.g., psychiatric disorders, cancer, seizures, or disorders of the GI tract, liver, kidney, respiratory system, endocrine system, hematological system, neurological system, or cardiovascular system, or subjects who have a congenital abnormality in metabolism.
2. Clinically significant illness, in the opinion of the PI/designee, that requires medical treatment within 8 weeks prior to dosing, or a clinically significant infection that requires medical treatment within 4 weeks prior to dosing.
3. Any history of GI surgery that may affect PK profiles of CT1812, e.g., hepatectomy, nephrectomy, gastric bypass, digestive organ resection. Subjects with a history of appendectomy may be included at the discretion of the PI/designee and Sponsor.
4. Has evidence of a clinically significant abnormality in physical examination findings, vital signs, or clinical laboratory determinations (congenital nonhemolytic

hyperbilirubinemia [e.g., suspicion of Gilbert's syndrome is not acceptable]) at the Screening visit or Check-in.

5. Has a clinically significant ECG abnormality, including a marked prolonged QT interval corrected by Fridericia's method (QTcF; e.g., a repeated demonstration of a QTcF interval >450 msec) at the Screening visit or Check-in, or a family history of prolonged QTc syndrome or sudden death or angina, or has history of congestive heart failure, poorly controlled hypertension, clinically significant arrhythmia, hypotension, any form of heart block (history of or on ECG at the Screening visit or Check-in), bundle branch block, symptomatic ectopy, unstable arrhythmias including atrial fibrillation, frequent supraventricular or ventricular ectopy, or a PR >210 msec or QRS duration >120 msec on ECG at the Screening visit or Check-in.
6. Estimated creatinine clearance <80 ml/min/1.73 m² at the Screening visit by Chronic Kidney Disease Epidemiology Collaboration (CKD-EPI) formula.
7. Known history of clinically significant allergy to CT1812 or excipients at the Screening visit.
8. Has been diagnosed with acquired immune deficiency syndrome, or tests positive for human immunodeficiency virus (HIV), Hepatitis B virus surface antigen (HBsAg), or Hepatitis C virus (HCV) at the Screening visit.
9. Has a history of alcohol use disorder within the 2 years before the Screening visit.
10. Positive urine drug or alcohol results at the Screening visit or Check-in.
11. Positive cotinine result at the Screening visit.
12. Unable to refrain from or anticipates the use of:
 - Any drugs, including prescription and non-prescription medications, herbal remedies, or vitamin supplements beginning 14 days prior to dosing except for those allowed in [Section 11.4.1](#).
 - Any drugs known to be significant inducers of CYP2D6 and CYP3A4 and/or P-gp, including St. John's Wort, for 28 days prior to dosing. Appropriate sources (e.g., Flockhart TableTM) will be consulted to confirm lack of PK/pharmacodynamic interaction with study drug.
13. Donation of blood or significant blood loss within 56 days prior to dosing.
14. Plasma donation within 7 days prior to dosing.
15. Poor peripheral venous access.
16. Recent history (within 2 weeks of Day -1) of abnormal bowel movements, such as diarrhea, loose stools, or constipation.

CONFIDENTIAL

CT1812, CA35306, Final Protocol, Amendment 1_15Dec2021

17. Has exposure to significant diagnostic or therapeutic radiation (e.g., serial X-ray, computed tomography scan, barium meal) or current employment in a job requiring radiation exposure monitoring within 12 months prior to Check-in.
18. Has participated in a radiolabeled drug study where exposures are known to the PI within the previous 3 months prior to admission to the clinic for this study or participated in a radiolabeled drug study where exposures are not known to the PI within the previous 6 months prior to admission to the clinic for this study. The total 12-month exposure from this study and a maximum of 3 other previous radiolabeled studies within 3 to 12 months prior to this study will be within the CFR recommended levels considered safe, per United States (US) Title 21 CFR 361.1 i.e., less than 5000 mrem whole-body annual exposure with consideration given to the half-lives of the previous radiolabeled study drugs received.
19. Has previously participated in a CT1812 investigational study.
20. Evidence or history of active suicidal thoughts (Type 4 or 5 on the C-SSRS) in the 6 months preceding the screening visit; or have a history of a suicide attempt in the previous 2 years, or more than 1 lifetime suicide attempt; or are at serious suicide risk per the PIs clinical judgment.
21. Has any condition that would, in the opinion of the PI/designee or Sponsor, make the subject unsuitable for the study or is, in the opinion of the PI/designee, not likely to complete the study for any reason.
22. Participation in another clinical study within 30 days prior to dosing. The 30-day window will be derived from the date of the last blood collection or dosing, whichever is later, in the previous study to Day 1 of the current study.

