13.3.4 Urine Sampling and Processing

Urine for determination of TRA and metabolite profiling will be collected at the specified intervals delineated in the Study Events Flow Chart ([Section 6](#)).

Prior to the predose sample collection, each subject will be instructed as to urine collection methods. All urine during an interval is to be collected.

On Day 1, a spot collection will be obtained prior to dosing for the predose sample. Subjects will be asked again to empty their bladder within approximately 15 minutes prior to dosing, and no urine will be collected at this time unless it is needed for the predose sample. Only one predose urine sample will be collected on Day 1.

Subjects will be encouraged to void at the end of each collection interval. If they do void at any time during the collection interval, the time should be documented. Should this be the case, subjects need to void again at the end of the collection period, as scheduled. However, should subjects be unable to void, this will be documented as well.

Urine will be refrigerated during the collection intervals. At the end of each interval, urine will be pooled and thoroughly mixed. Total urine volume will be weighed and recorded.

Predose samples should be handled, processed, analyzed, and stored separately away from the postdose samples to avoid cross contamination.

Instructions for urine sampling, collection, processing, and sample shipment will be provided separately.

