13.3.6 Fecal Sampling and Processing

Fecal samples for the determination of TRA and metabolite profiling will be collected at the specified intervals delineated in the Study Events Flow Chart ([Section 6](#)).

The predose fecal sample is to be obtained within 48 hours prior to dosing. Subjects will be asked to bring a fecal sample at Check-in (if produced within 48 hours prior to dosing). Feces produced between Check-in and dosing will also be collected as a predose sample with the sample produced nearest to dosing to be retained as the only predose sample.

All fecal samples will be collected and stored individually for analysis of TRA and for metabolite profiling. The samples will be weighed at the time of collection. Multiple fecal samples from a given subject in a given interval will be pooled into a single sample at the time of homogenization.

Predose samples should be handled, processed, analyzed, and stored separately away from the postdose samples to avoid cross contamination.

Instructions for fecal sampling, collection, processing, and sample shipment will be provided separately.

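### Exclusion criterion 18 sets no limit on residual 14C from earlier labeled studies, and the supplied documents do not say how predose radioactivity is used

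*Protocol*

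**What the plan says.** Criterion 18 in Protocol Section 11.2 has three parts.

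- A 3-month window: "Has participated in a radiolabeled drug study where exposures are known to the PI within the previous 3 months prior to admission".
- A 6-month window: "participated in a radiolabeled drug study where exposures are not known to the PI within the previous 6 months prior to admission".
- A limit on what remains. The total over 12 months, from this study plus "a maximum of 3 other previous radiolabeled studies within 3 to 12 months prior to this study", must be "less than 5000 mrem whole-body annual exposure with consideration given to the half-lives of the previous radiolabeled study drugs received".

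The criterion speaks of radiolabeled studies in general. It names no isotope, no earlier administered activity and no residual level.

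The radioactive dose here is about 1 µCi with 300 mg CT1812 (Section 8.2.2). Section 8.2.1 says TRA will be measured by accelerator mass spectrometry (AMS); Section 13.3.10 allows liquid scintillation counting or AMS.

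The Study Events Flow Chart (Section 6) schedules predose TRA in whole blood, plasma, urine and feces. For urine, "On Day 1, a spot collection will be obtained prior to dosing for the predose sample". For feces, one sample is kept, "with the sample produced nearest to dosing to be retained as the only predose sample". Sections 13.3.1, 13.3.4 and 13.3.6 ask that predose samples be handled and analyzed apart from later ones to avoid cross contamination. They do not say what is done with the result.

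Section 14.3.1.2 defines mass balance as urine plus fecal TRA relative to the administered radioactive dose, with an allowance for emesis. Neither that formula nor the TRA parameters in Sections 13.3.2, 13.3.5 and 13.3.7 contains a predose term. The supplied SAP covers only the plasma assay of CT1812 and M6.

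**The concern.** A millirem cap protects the subject from radiation. It does not protect the baseline of an assay that must account for a 1 µCi dose. A man who took a conventional 14C dose 3 to 12 months before admission can meet criterion 18 and still be excreting small amounts of that label. Unless predose radioactivity is removed, TRA measurement cannot tell it from the study dose.

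The affected quantities belong to the primary objectives. Recovery in urine and feces would be biased upward, the terminal TRA curve would flatten (longer half-life, larger AUC), and the CT1812-to-TRA ratio would fall. Section 8.2.1 expects more than 90% of the radioactivity to be eliminated within 168 h, so a bias of several points could hide incomplete recovery in a subject.

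There is also a wording conflict inside the criterion. It allows studies with exposure unknown to the PI once 6 months have passed, yet requires the 12-month total to be below the cap. For an unknown exposure 6 to 12 months back, that total cannot be calculated.

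**Working it through.** **Inputs from the Protocol.** Dose 1 µCi with 300 mg; effective dose 0.036 mrem per 1 µCi; limit 3000 mrem (Section 8.2.2). Cap 5000 mrem (criterion 18). Collection 168 h = 7 days. Eight enrolled, for 6 with complete data (Section 14.1).

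**Inputs assumed (not in the documents).** The earlier label is 14C; earlier dose D; fraction r in a slowly cleared pool; half-life h of that pool; one exponential; all residue leaves in urine or feces.

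**1. The plan's own figure.** 0.036/3000 = 0.0012%. It reproduces.

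**2. The cap against this dose.** 5000/0.036 ≈ 138,900 µCi, about 139,000 times the study dose on this drug's own conversion. The cap does not bind at any level that matters to the assay.

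**3. Sensitivity.** 1 µCi = 1000 nCi, so 10 nCi excreted in 168 h reads as 1 percentage point of recovery. Each 1 nCi reads as 300 mg/1000 = 300 µg-equivalents of CT1812.

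**4. Carry-over from one earlier study 90 days before dosing.**
Added points = 100 × D × r × 0.5^(90/h) × (1 − 0.5^(7/h)) / 1 µCi. With D = 100 µCi:

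| h (days) | 0.5^(90/h) | 1 − 0.5^(7/h) | r = 0.1% | r = 1% | r = 5% |
|---|---|---|---|---|---|
| 7 | 0.0001 | 0.5000 | 0.00 | 0.01 | 0.03 |
| 10 | 0.0020 | 0.3844 | 0.01 | 0.08 | 0.38 |
| 30 | 0.1250 | 0.1493 | 0.19 | 1.87 | 9.3 |
| 60 | 0.3536 | 0.0777 | 0.27 | 2.75 | 13.7 |
| 120 | 0.5946 | 0.0396 | 0.24 | 2.36 | 11.8 |

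With D = 50 µCi every entry halves. With D = 1 µCi (a microtracer) every entry is divided by 100, so none exceeds 0.14 points.

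**5. Three earlier studies.** With D = 100 µCi and r = 5% at 91, 182 and 273 days, summing the same expression gives +14.7 points for h = 40 days and +22.2 for h = 80 days (one study at 91 days: +11.8 and +13.4).

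**6. Effect on the mean (one affected subject, one earlier study).** At r = 1%: 1.87/8 = 0.23 to 2.75/6 = 0.46 points. At r = 5%: 9.3/8 = 1.2 to 13.7/6 = 2.3 points.

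**7. What a 12-month lookback does.** Replacing 90 by 365 days at D = 100 µCi, r = 5%: h = 60 days falls from 13.7 to 0.6 points; h = 120 days from 11.8 to 2.4.

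**8. What predose subtraction does.** Take D = 100 µCi, r = 5%, h = 40 days, 91 days earlier. Body burden B = 5 × 2^(−91/40) = 1.033 µCi. Excreted in 7 days: 1.033 × (1 − 2^(−7/40)) = 0.118 µCi, or +11.8 points. A constant predose rate over 7 days removes 1.033 × (0.693/40) × 7 = 0.125 µCi, leaving −0.7 points. For three studies the change is from +14.7 to −0.9. This assumes the predose rate is measured without error.

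**The case against.** Five points can be made in the plan's defense.

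- **The windows act as a washout.** A reader might infer that earlier labels are limited by radiation safety alone. That is too strong: whatever their purpose, the 3- and 6-month windows remove labels cleared with half-lives of days, as the 7- and 10-day rows show. This stands.
- **Baselines are collected.** Predose TRA is scheduled in all four matrices, including whole blood and plasma, where the TRA half-life and AUC are derived. This stands. The gap is a rule for using them.
- **A correction may be written elsewhere.** Section 13.3.10 leaves analytical specifics to separate documents, and Section 14.3 leaves detailed methods to a SAP prepared by the clinical contractor. The supplied SAP is a bioanalytical plan that does not cover TRA. Silence in these two documents does not show that correction is unplanned. This stands, and it makes the subtraction part closer to a missing detail than an error.
- **The size is assumed.** Earlier dose, retention and half-life are not in the documents, and the earlier label need not be 14C. The ratio of 139,000 might suggest gross contamination, but it compares administered activity, not residue, and applies this drug's conversion to unknown compounds. It shows only that the cap is irrelevant to the assay.
- **Subtraction might make a lookback redundant.** In the model it removes nearly all of the bias. In practice it would rest on one spot urine and one fecal sample, a noisy basis for seven days of excretion. The lookback reduces what must be subtracted, so it still adds something.

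**Conclusion.** The point holds as a cheap improvement to a stated eligibility rule, not as a demonstrated bias. Criterion 18 allows entry after a conventional 14C dose 3 to 12 months earlier without any residual-14C limit, and the mass-balance formula as written would count that residue as recovered dose.

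The effect can be large for an individual and is modest for the mean: up to 9–14 points in one subject and about 2 points in the mean if 5% of 100 µCi was retained with a half-life of 30 to 120 days; 1.9–2.8 points and under half a point at 1%; negligible at 0.1%, for half-lives of days, or after a microtracer. Several high-dose 14C studies in one man could take his figure above 20 points under the 5% assumption. All of these sizes depend on the assumed earlier dose, retention and half-life.

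The documents do not support a conclusion that enrolled subjects will carry residual 14C, or that predose values will be ignored.

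The conflict over unknown exposures is separate. It concerns the radiation-safety wording and adds no weight to the assay concern.

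**What to change.** 1. **Criterion 18:** add, on assay grounds and apart from the radiation cap, that a subject may not have taken part in a 14C-labeled study within 12 months before Check-in. Twelve months matches the window in criterion 17. It does not remove every slow residue (2.4 points remain in the 120-day, 5% case), so items 2 and 3 are still needed.
2. **Section 14.3.1:** state that TRA in each matrix is net of the subject's own predose value, or cite the document that already says so.
3. **Sensitivity summary:** repeat the mass-balance and TRA summaries without any subject whose predose TRA concentration exceeds a prespecified level above natural 14C background. Use a concentration, because a spot urine has no collection interval and cannot give a percentage of dose per day without an assumed urine volume.
4. **Separately,** reconcile the part of criterion 18 that admits unknown exposures after 6 months with the part that requires the 12-month total to be under the cap.

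The cost is protocol and SAP wording and a slightly smaller screening pool for 8 healthy volunteers. No new samples are needed, since the predose samples are already scheduled.
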